7. INVESTIGATION PLAN

7.1 Overall Study Design and Plan Description

This will be a randomized, placebo-controlled, double-blind, multicenter, Phase 2 study in subjects with Type 2 diabetes, UACR 200 to 3000 mg/g and eGFR ≥ 30 ml/min/1.73m².

Potentially eligible subjects will attend an initial Screening Visit (Visit 1) and sign an informed consent document. After the subject's medical history is reviewed and inclusion/exclusion criteria for the trial assessed, urine and blood samples will be obtained and sent to a [REDACTED].

Subjects who have a UACR 200 to 3000 mg/g and eGFR ≥ 30 ml/min/1.73m² and meet all other protocol-specified eligibility criteria at Visit 1 will return for Visit 2. At Visit 2, subjects will have a physical examination including triplicate blood pressure measurements, a standard 12-lead ECG, provide blood samples for repeat eGFR, and submit 2 consecutive day mid-stream first-morning void urine samples for Baseline UACR determination for confirmation of eligibility. Subjects will be given study medication to be used during a single-blind, placebo run-in phase and instructed to return their study medication to the site at Visit 3. All pre-randomization study visits will be completed in ≤ 6 weeks. Study medication will be self-administered by the subject qd. Study medication should be taken in the morning at about the same time each day, and taken with food (breakfast or a snack) rather than on an empty stomach beginning on the day after Visit 2.

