7.3.1 Inclusion Criteria

To be eligible to participate in the study, subjects must meet the following criteria:

1. Males or females using a highly effective birth control method or not of childbearing potential who are at least 18 years of age at Visit 1
2. Has Type 2 diabetes and has been treated with ≥ 1 glucose-lowering medication for at least 12 months prior to Visit 1
3. Treatment with at least the minimal recommended dose of an angiotensin converting enzyme inhibitor (ACEI) or an angiotensin II receptor blocker (ARB), but not both, for at least 3 months prior to Visit 1, without any adjustments to this therapy for at least 4 weeks prior to the Visit 1
4. Willingness and ability to provide written informed consent prior to any study-related procedures and to comply with all study requirements
5. Urinary albumin-to-creatinine ratio 200 to 3000 mg/g at Visit 1 and Visit 2. The average of the 2 consecutive day mid-stream, first-morning void UACR results will be used at Visit 2
6. Estimated glomerular filtration rate ≥ 30 ml/min/1.73m² (calculated using the Chronic Kidney Disease Epidemiology Collaboration [CKD-EPI] equation) at Visit 1 and Visit 2
7. Compliance (based on pill count) of $\geq 80\%$ during the single-blind, placebo run-in phase of the study

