7.5.3 Single-Blind, Placebo Run-in Phase (Visit 2): Day -14 ± 4 Days

The following information and procedures will be recorded and performed for all eligible subjects at

Visit 2:

- pre-Visit 2 call for reminder of urine collection
- confirmation of subject eligibility based on inclusion/exclusion criteria
- contact IXRS
- urine sample for UACR (2 consecutive day mid-stream, first-morning void urine samples to be collected at the subject's home on the morning before and the morning of Visit 2)
- serum chemistry profile (including sUA and serum creatinine to calculate eGFR); see [Appendix A](#) for the evaluations to be performed
- viral serologies
- thyroid hormones
- lipid panel
- adverse event recording
- prior/concomitant medication review
- vital signs, consisting of supine blood pressure, supine pulse rate, and oral body temperature
- resting 12-lead ECG
- physical examination
- dispense treatment kit for 2-week placebo run-in
- dispense urine collection supplies (for collection of 2 consecutive day first-morning void urine samples on the morning before and the morning of Visit 3)
- before leaving the site, each subject will be given a card to carry at all times in case of an emergency outside the site. The card gives details of the study number, start and end date of the subject's involvement in the study, subject details, name of the relevant study physician, and the address and telephone number of the site. Subjects may destroy this card 4 weeks after they have completed the study

Single re-testing of laboratory parameters or other assessments may be performed at the Investigator's discretion.

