7.10.2 Subject Populations Analyzed

The **All Subjects Population** will consist of any subjects who enrolled in the study (signed informed consent) and had study assessments recorded on the database as per the protocol.

The **Safety Population** will consist of all randomized subjects who received at least one study medication tablet or capsule.

The **Modified Intention-to-Treat (mITT) Population** will be used for the efficacy analysis and will consist of all subjects according to their randomization scheme regardless of whether they experienced protocol deviations. The last post randomization UACR will be carried forward (LOCF) for subjects who did not have a Week 12 UACR determination. Randomized subjects with no post randomization UACR will be excluded from the mITT analysis.

The **Per Protocol Population** will be used as a sensitivity analysis for the primary efficacy endpoint and will consist of all subjects according to their randomization scheme who experienced no major protocol deviations.

The **PK Population** will consist of all subjects who received at least one dose of TMX-049 and have evaluable PK data.

All protocol deviations that occur during the study will be considered prior to database lock for their severity/impact and will be taken into consideration when subjects are assigned to analysis populations. Details of subject assignment to the analysis populations will be listed.

Efficacy will be analyzed using the mITT Population (primary analysis) and the Per Protocol Population (supportive analysis), and safety will be analyzed using the Safety Population. Changes from Baseline will utilize values obtained at Visit 3 (the randomization visit) except for the change from baseline in UACR.

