6.1 Time points and Visit Windows

Day 0 is defined as the Baseline/Randomization visit (Study Visit 3). Day 1 is the first day of treatment. Relative days after Day 1 are calculated as (assessment date – Day 1 date) + 1. Relative days prior to Day 1 are calculated as (assessment date – Day 1 date).

The visit windows defined in the following table will be used for the by-visit analyses of the primary, the secondary and other endpoints. All other analyses will use the nominal study visit as defined in the study schedule and eCRF.

If there are multiple visits (scheduled or unscheduled) within a visit window, the measurement closest to the target day of the visit will be used in the analysis. If the measurements are equally distant to the target day, then the later one will be used in the analysis.

Time Point (Target Study Day)	Study Day Range for UACR*	Study Day Range for Serum Chemistry, Hematology, Lipid Panel, Urinalysis, Blood and Urine Samples for Biomarkers, Vital Signs	Study Day Range for ECG, Physical Examination	Study Day Range for HbA1C
Baseline	≤ 1	≤ 1	< 1	≤ 1
Week 2 (Day 14)	2 – 21	2 - 21		
Week 6 (Day 42)	22 – 63	22 - 63		
Week 12/ET (Day 84)	64 – 104	64 – 104	≥ 1	> 1
Week 12/ET + 28 Days (Day 112)	≥ 105	≥ 105		

*: This is for the first morning void UACR sample collection.

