7.6.5 Secondary Efficacy Endpoints Analysis

Analysis of the secondary efficacy endpoints will be based on mITT population and PP population. Descriptive statistics for secondary efficacy endpoints will be presented by treatment group and by study visit where appropriate. All post-baseline data collected will be used in the analyses, including observations occurring after discontinuation of study drug.

7.6.5.1 Change in eGFR, UACR, and sUA from Baseline to Study Weeks 2, 6, 12/ET, and Follow-up Visit

For each of these secondary efficacy endpoints, the ANCOVA model using LOCF described for the primary efficacy endpoint in **Section 7.6.1** will be fitted for the change from Baseline to each specific timepoint, ie, Study Week 2, Week 6, Week 12, and Follow-up Visit.

The MMRM and all observed data (excluding data collected at Follow-up visit) described for the primary efficacy endpoint in **Section 7.6.2** will be fitted for each of these endpoints also.

Note: In the above ANCOVA and MMRM models, Baseline eGFR will be included as a covariate to model change in eGFR from Baseline.

For each of these endpoints, 3 figures will be generated by treatment group: figure to present the mean change from Baseline by visit; figure to present the LS mean change from Baseline to Study Week 12 from the ANCOVA model, and figure to present the LS mean change from Baseline to each post-baseline study weeks from the MMRM.

In addition, the following scatter plots will be generated by treatment group:

- Change in UACR at Study Week 12 from Baseline versus Baseline UACR

- Change in UACR at Study Week 12 versus change in eGFR at Study Week 12 from Baseline
- Change in UACR at Study Week 12 from Baseline versus Baseline eGFR
- Change in UACR at Study Week 12 from Baseline versus Baseline sUA
- Change in UACR at Study Week 12 from Baseline versus Change in sUA at Study Week 12
- Change in UACR at Study Week 12 from Baseline versus Baseline BMI
- Change in UACR at Study Week 12 from Baseline versus Baseline SBP
- Change in UACR at Study Week 12 from Baseline versus Baseline HbA1C
- Change in UACR at Study Week 12 from Baseline versus Baseline 8-OHdG
- Change in UACR at Study Week 12 from Baseline versus Baseline hs-CRP
- Change in UACR at Study Week 12 from Baseline versus Baseline sTNFR1
- Change in eGFR at Study Week 12 from Baseline versus Baseline eGFR
- Change in eGFR at Study Week 12 from Baseline versus Baseline sUA

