7.7.2 Laboratory Evaluations

Data for the following hematology, blood chemistry, lipid profile, and urinalysis received from central laboratory will be listed and summarized by treatment group and visit. If data for any additional analytes are also received then these will be listed only.

All summaries of laboratory test results will be presented in International System of Units (SI) and conventional units. Out-of-reference-range values will be flagged as high (H) or low (L) in the listings.

For analysis purposes, values preceded by a "<" or a ">" sign (ie, those below or above the limits of quantification) will be considered equal to the lower or upper limit of quantification, respectively.

Laboratory evaluations measured on a continuous scale will be summarized by visit using standard descriptive statistics for the Safety population. Changes from Baseline will also be summarized. For analysis by visit, the nominal study visits will be utilized.

Statistical Analysis Plan

Teijin America, Inc.
TMX-049DN-201

Qualitative urinalysis laboratory results will be summarized for Baseline and all scheduled post-baseline study weeks as the number and percentage of patients having either positive or negative results. Missing category will be reported if there is more than 1 patient reported in any treatment group.

For each laboratory analyte, the Baseline value will be defined as last scheduled or unscheduled value collected prior to the first dose of treatment.

For hematology and serum chemistry, shift tables presenting movement in and out of reference range from Baseline to each scheduled post-Baseline visit will be provided for each treatment group.

Mean change from Baseline with standard deviation bars will be plotted by visit for select laboratory parameters for the Safety Analysis Set.

The lab parameters collected are presented in the following table:

Statistical Analysis Plan

Teijin America, Inc.
TMX-049DN-201

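### The eGFR models adjust for one Baseline eGFR and leave out the Visit 2 eGFR; adding it as a second covariate would probably narrow the interval at almost no cost

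*SAP*

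**What the plan says.** A note in SAP 7.6.5.1 states that in both models for this endpoint "Baseline eGFR will be included as a covariate to model change in eGFR from Baseline". That is one baseline covariate, alongside treatment and the two randomisation strata (plus timepoint and its interaction with treatment in the MMRM).

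Baseline is a single measurement wherever the documents define it:

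- Protocol 7.10.2: "Changes from Baseline will utilize values obtained at Visit 3 (the randomization visit) except for the change from baseline in UACR".
- SAP 7.7.2: "For each laboratory analyte, the Baseline value will be defined as last scheduled or unscheduled value collected prior to the first dose of treatment".
- SAP 6.1, on several results falling in one window: "the measurement closest to the target day of the visit will be used in the analysis". One value is picked and nothing is averaged.

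An earlier eGFR exists. Under Protocol 7.1, subjects at Visit 2 "provide blood samples for repeat eGFR". Protocol 7.5.3 lists at that visit a "serum chemistry profile (including sUA and serum creatinine to calculate eGFR"). Protocol 7.3.1 requires "Estimated glomerular filtration rate ≥ 30 ml/min/1.73m² (calculated using the Chronic Kidney Disease Epidemiology Collaboration [CKD-EPI] equation) at Visit 1 and Visit 2", so every subject who properly meets the entry criteria has a Visit 2 value. Protocol 7.6.1.2 derives eGFR by CKD-EPI from the creatinine in the chemistry profile, so the method is the same at both visits. Visit 2 falls at Day -14 ± 4, before randomised drug.

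**The concern.** A single creatinine-based eGFR carries visit-to-visit noise. A second measurement taken before randomisation helps to separate a subject's underlying level from that noise, and so explains more of the variation at Week 12. The plan collects such a measurement in every eligible subject but uses it only for eligibility. For UACR, by contrast, SAP 7.6.1 averages two urine samples per visit.

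What is at stake is the width of the interval around the eGFR difference. The effect on eGFR is the first secondary objective listed, with about 40 subjects per group. The sample size was set for UACR, and no precision target is given for eGFR.

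**Working it through.** **The plan's own figure.** The only power statement (Protocol 7.10.1, SAP 2.3) concerns UACR. A two-sided 0.05 t-test with 40 per group, difference 0.431 and SD 0.670 has power 0.811, so the stated figure of more than 80% holds. It says nothing about eGFR.

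**Inputs.** From the documents: 40 per group, baselines at Visits 2 and 3, outcome at Week 12. Assumed, because the documents give nothing: between-subject SD 20, visit noise SD *s* of 4 to 6, and true 12-week change SD *d* of 0, 4 or 6, all in ml/min/1.73m². The strata covariates are ignored. The calculation is for the Week 12 ANCOVA and only approximates the MMRM. Once baseline is a covariate, the residual variance is the same whether the outcome is the change or the Week 12 value.

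**Equal correlation of both visits with Week 12.**

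- One baseline: V1 = 400 + s² + d² − 400²/(400 + s²)
- Visits 2 and 3: V2 = 400 + s² + d² − 2·400²/(800 + s²)
- SE of a treatment difference = √(2V/40)

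For s = 4 and d = 4: V1 = 432 − 384.62 = 47.38 and V2 = 432 − 392.16 = 39.84. The cut is 1 − 39.84/47.38 = 15.9%.

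| s | d | V1 | V2 | Cut in residual variance | SE, one baseline | SE, two |
|---|---|---|---|---|---|---|
| 4 | 0 | 31.38 | 23.84 | 24.0% | 1.25 | 1.09 |
| 4 | 4 | 47.38 | 39.84 | 15.9% | 1.54 | 1.41 |
| 4 | 6 | 67.38 | 59.84 | 11.2% | 1.84 | 1.73 |
| 6 | 0 | 69.03 | 53.22 | 22.9% | 1.86 | 1.63 |
| 6 | 4 | 85.03 | 69.22 | 18.6% | 2.06 | 1.86 |
| 6 | 6 | 105.03 | 89.22 | 15.0% | 2.29 | 2.11 |

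At s = 4 the 95% half-width shrinks by 1.96 × 0.128 = 0.25 (d = 4) or 1.96 × 0.106 = 0.21 (d = 6). The equivalent gain in sample size is 47.38/39.84 = 1.19 or 67.38/59.84 = 1.13.

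**Correlation that decays with time.** Let true eGFR follow a random walk, with variance d²·2/12 accruing in the two weeks between Visits 2 and 3. For s = 4 and d = 6 that is 36 × 2/12 = 6. The residual variance falls from 67.39 to 61.15, a cut of 9.3%. The other cases give 14.6% (s = 4, d = 4), 17.8% (s = 6, d = 4) and 13.7% (s = 6, d = 6).

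**Small noise relative to change.** With s = 3 and d = 8 the cut is 5.3% under equal correlation and 3.2% with decay. It can also be found from the correlations a (Visit 3 with Week 12), b (Visit 2 with Week 12) and c (Visit 2 with Visit 3). With R² = (a² + b² − 2abc)/(1 − c²), the cut is 1 − (1 − R²)/(1 − a²). A plain average of the two visits is shown for comparison; a minus sign means a larger residual variance.

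| a / b / c | Separate covariates | Average of the two visits |
|---|---|---|
| 0.90 / 0.88 / 0.93 | 7.2% | 5.7% |
| 0.90 / 0.87 / 0.95 | 1.2% | −3.5% |
| 0.90 / 0.864 / 0.96 | 0% | −8.5% |

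In the last row 0.864 = 0.90 × 0.96, which in the decay model above means a Visit 3 value free of measurement noise. It is a boundary case.

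**The case against.** The strongest reply is that nothing here is wrong. Adjusting for one baseline is conventional, pre-specified and gives valid inference, and almost any trial with screening laboratory tests could receive this comment. That stands, and it limits the point to an optional gain.

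The second reply is that every input is assumed. Visit 3 is closer in time to Week 12, and Protocol 7.4.6.1 allows antihypertensives and diuretics to be changed after Visit 2 when clinically necessary, which could weaken the link between Visit 2 and Week 12. This also stands, and it is why the lower end of the range is a few percent or less.

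Four stronger readings are tempting but not supported:

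- *A reader might infer that the plan throws away 11 to 24% of the attainable variance reduction.* Those figures are cuts in residual variance. With equal correlation r and no true change, one baseline removes r² of the variance and two remove 2r²/(1 + r), so the share forgone is (1 − r)/2. That is 7.5% at r = 0.85 and 1.5% at r = 0.97. The single baseline already secures most of the benefit.
- *A reader might treat eGFR as a key secondary endpoint or the main renal-safety measure.* SAP 3.2 lists five unranked secondary endpoints, and the safety endpoints in SAP 3.3 do not single out eGFR.
- *A reader might equate the gain with about 30% more subjects.* That follows from 31.38/23.84 = 1.32, which assumes no true between-subject change over 12 weeks.
- *A reader might think averaging the two visits would do as well.* The last table shows that it can increase the variance.

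**Conclusion.** This is a free improvement and the current analysis is valid. The eGFR models omit a measurement that is already collected, precedes randomisation and very probably predicts the outcome. For a between-subject SD of 20, noise SD of 4 to 6 and true-change SD of 4 to 6, the expected cut in residual variance is about 11 to 19%. The upper limit is about 24% with no true change, the range with decaying correlation is roughly 9 to 18%, and the gain almost vanishes when noise is small relative to true change. At noise SD 4 the SE of the difference moves from about 1.54 to 1.41, or from 1.84 to 1.73. None of these inputs comes from the documents, so the direction of the gain is more certain than its size.

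**What to change.** Before unblinding, replace the note in SAP 7.6.5.1 with wording such as:

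*Baseline eGFR (as defined in the SAP) and Visit 2 eGFR (the last Visit 2 value, including any permitted repeat) will be included as separate covariates in the ANCOVA and MMRM for change in eGFR. If Visit 3 is missing and Visit 2 serves as Baseline, that value is used for both.*

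The parenthesis on repeats is needed because Protocol 7.3 and 7.5.3 allow one retest at Visit 2. The last sentence is needed because, under SAP 7.7.2, Visit 2 can become the Baseline; without it such a subject would lack a covariate. Do not average the two visits. Keep the reference for change as it is, so the endpoint is unaffected.

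The cost is one sentence and one degree of freedom. With 120 subjects, the ANCOVA with intercept, two treatment terms, two strata terms and Baseline eGFR has 120 − 6 = 114 residual degrees of freedom, and 113 after the change. No new data are needed.

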7.10.1 Determination of Sample Size

Approximately 132 subjects will be randomized at a 1:1:1 ratio to each of the 3 treatment groups (40 mg TMX-049, 200 mg TMX-049, and placebo). Assuming that 10% of all randomized subjects will not be included in the primary endpoint analysis, this would result in approximately 40 subjects per treatment group for inclusion in the primary endpoint assessment.

A sample size of 40 per group will have more than 80% power on the primary endpoint assessment to detect a difference in means of 35% reduction (-0.431 for log-transformed value) of UACR assuming that the common standard deviation (SD) is 0.670 (log-scale) using a 2-group t-test with a 0.050 two-sided significance level.

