5.2 Randomized Population

All randomly assigned subjects will be included in the Randomized population. Randomized subjects are analyzed according to their randomized treatment.

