5.4 Modified Intent-to-treat Population

The mITT population will consist of all randomized subjects who have at least 1 post randomization UACR assessment. Subjects in the mITT population will be analyzed according to their randomized treatment.

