5.5 Per-Protocol Population

The PP population will consist of all subjects in the mITT population who do not experience any important protocol deviations leading to exclusion from the PP population. Subjects in the PP population will be analyzed according to their randomized treatment.

Protocol deviations are defined as any change, divergence, or departure from the study design or procedures defined in the study protocol. Important protocol deviations are a subset of protocol deviations and may significantly impact the correctness, accuracy, and/or reliability of the study data or that may significantly affect a subject's rights, safety, or well-being. **Section 5.5.1** details the deviations.

All protocol deviations that occur during the study will be considered prior to database lock (DBL) for their severity and impact.

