7.1 General Principles

All data processing, summarization and analyses will be performed using the Hosted SAS (d-Wise) Environment / Version 9.4 (or later) of the SAS[®] (SAS Institute, Cary, NC) statistical software package.

Unless specified otherwise, data will be displayed using the following treatment group labels, in the order presented:

- Placebo
- TMX-049 40 mg QD
- TMX-049 200 mg QD
- TMX-049 Overall

All data collected will be presented in listings by treatment group, center, subject, and visit (where applicable), unless otherwise specified.

Data will be presented in summary tables by treatment group, assessment, and visit (where applicable).

The category "Missing" will be presented if the number missing is greater than zero for at least 1 treatment group.

Descriptive summary statistics for continuous variables will include the number of observations (N), mean, standard deviation (SD), median, minimum, and maximum. For UACR of original scale, the geometric mean, geometric coefficient of variation (CV), and CV will also be provided.

Descriptive summary statistics for categorical variables will include frequency counts and percentages [n (%)]. Unless stated otherwise in the table shells, the denominator for percentage calculations will be the number of subjects in the pertinent analysis population.

Dates will be displayed as DDMMYYYY.

Analysis and summarization of treatment group comparisons for the primary and secondary efficacy endpoints will be reported in their original measurement units and converted values to accommodate regulatory review by FDA and external authorities, where appropriate.

All significance tests will be 2-sided and use a 0.05 α -level.

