- Change in sUA at Study Week 12 versus change in eGFR at Study Week 12 from Baseline

7.6.5.2 Proportion of Subjects with >30% Reduction from Baseline to Study Week 12 in UACR

The frequency and percent of subjects with >30% reduction from Baseline to Study Week 12 in UACR will be presented by treatment group. Subjects with missing observations at Study Week 12 are imputed as non-responders for this analysis.

Fisher's exact test will be performed between each TMX-049 group and the placebo group and the exact p-value from each test will be provided. The difference in the percentage of responders between each treatment group and the Placebo group and the exact 95% CLs based on Clopper-Pearson method will also be provided.

Furthermore, the association between having UACR reduction greater than 30% from Baseline to Study Week 12 and the treatment group will be assessed by Logistic regression model. The model will use the incidence of subjects with >30% reduction as the dependent variable, the randomized treatment group, randomization strata of sUA (<6.0 vs \geq 6.0 mg/dL), and UACR (200 to <300 mg/g vs 300 to \leq 3000 mg/g) levels as independent variables, Baseline UACR and Baseline sUA levels as covariates. The estimated odds ratio (and 95% CL) of having >30% reduction versus not having >30% reduction in URCA in any active TMX-049 group versus Placebo group, will be provided.

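### The >30% UACR responder analysis counts a missing Week 12 as failure, but its mITT denominator drops randomised subjects who have no post-randomisation UACR

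*SAP*

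**What the plan says.** SAP 7.6.5.2 sets the missing-data rule for the responder endpoint: "Subjects with missing observations at Study Week 12 are imputed as non-responders for this analysis". That subsection names no population of its own, so the general rule at the start of SAP 7.6.5 applies: "Analysis of the secondary efficacy endpoints will be based on mITT population and PP population".

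Both populations require a post-randomisation value:

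- SAP 5.4: "The mITT population will consist of all randomized subjects who have at least 1 post randomization UACR assessment".
- Protocol 7.10.2: "Randomized subjects with no post randomization UACR will be excluded from the mITT analysis".
- SAP 5.5 nests PP inside mITT: "The PP population will consist of all subjects in the mITT population who do not experience any important protocol deviations".

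SAP 7.1 fixes the percentage base. Unless the table shells say otherwise, "the denominator for percentage calculations will be the number of subjects in the pertinent analysis population".

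SAP 5.2 also defines a wider set: "All randomly assigned subjects will be included in the Randomized population". No responder analysis uses it.

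**The concern.** The purpose of non-responder imputation is that every subject without an outcome counts as a failure, so the arms are compared as randomised. Here the rule reaches only subjects who have already supplied a post-randomisation UACR. Two subjects with the same outcome status, no Week 12 result, are handled in opposite ways according to when they were lost.

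The exclusion has a reason in the primary analysis, where LOCF needs a post-baseline value to carry forward. The responder analysis inherits it without needing it.

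At stake are the responder percentages, which are too high in any arm with such exclusions, and the difference between arms, which can shift either way if the exclusions are unequal. The primary endpoint is not touched by this rule.

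**Working it through.** **1. Who falls out of the denominator.** The first scheduled post-randomisation UACR is at Visit 4, Day 14 ± 4 (Protocol Table 2). Subjects who withdraw or stop treatment are asked to attend an early termination visit and an end-of-study visit (Protocol 7.3.3.3 and 7.5.5), and both collect UACR (Table 2). The three routes are:

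| Subject | In mITT? | Responder status |
|---|---|---|
| Lost after a Visit 4 UACR, no Week 12 value | Yes | Non-responder |
| Withdraws before Visit 4, gives a UACR at early termination or Visit 7 | Yes | Non-responder (see below) |
| Gives no UACR at Visit 4, early termination, Visit 7 or any other visit after randomisation | No | Not counted |

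For the second row, the SAP 6.1 windows keep Week 12 missing. An early termination by Day 18 lies in the Week 2 window (Days 2–21). Visit 7 then falls at the latest on Day 18 + 28 + 7 = 53, inside the Week 6 window (Days 22–63) and short of the Week 12 window (Days 64–104).

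**2. The plan's own sample-size figures.** From Protocol 7.10.1 and SAP 2.3: 132 randomised 1:1:1, 10% not analysed, effect −0.431, SD 0.670, two-sided 0.05.

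- 132/3 = 44 per arm; 132 × 0.9/3 = 39.6, or about 40.
- ln(0.65) = −0.4308, which matches −0.431.
- Normal approximation: 0.431/(0.670 × √(2/40)) = 2.877, and Φ(2.877 − 1.960) = 0.820. The noncentral t gives 0.811. Both agree with the stated power of more than 80%.

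The documents give no rate or power for the responder endpoint.

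**3. Illustrative responder rates.** Assumptions: log change is normal with SD 0.670, mean 0 on placebo and −0.431 on active, and every subject in mITT has a Week 12 value. A response is a change below ln(0.70) = −0.3567.

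- Placebo: Φ(−0.3567/0.670) = 29.7%.
- Active: Φ((−0.3567 + 0.431)/0.670) = 54.4%.
- Difference on mITT: 24.7 points.

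**4. Effect of counting all 44 per arm.** Excluded subjects become non-responders, so each rate is multiplied by (44 − excluded)/44. Differences use unrounded rates.

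| Excluded, active vs placebo | Active | Placebo | Difference (points) |
|---|---|---|---|
| 0 vs 0 | 54.4% | 29.7% | 24.7 |
| 1 vs 0 | 53.2% | 29.7% | 23.5 |
| 2 vs 0 | 51.9% | 29.7% | 22.2 |
| 4 vs 4 | 49.5% | 27.0% | 22.4 |
| 2 vs 6 | 51.9% | 25.7% | 26.3 |

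In whole counts, the 4 vs 4 case is 22/40 vs 12/40 on mITT (Fisher p = 0.041) and 22/44 vs 12/44 on all randomised (p = 0.048). The last row is there to show the reversal of direction, not as an expected pattern.

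**5. Can the excluded subjects be analysed?** Fisher's test needs only the arm and the imputed status. The logistic model in SAP 7.6.5.2 uses treatment, the strata from Visit 2, and Baseline UACR and sUA. These are scheduled before the first randomised dose, so they should normally exist.

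**The case against.** The strongest reply is that almost nobody will be excluded. A subject who withdraws early for an adverse event and attends either the early termination visit or Visit 7 is in mITT and already counts as a failure. That stands, and it rules out reading the SAP as if early withdrawals in general disappear. It does not reduce the number to zero: those visits take place only where feasible, and a subject who declines to return is telephoned instead (Protocol 7.5.5), which yields no UACR.

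A reader might also take the sentence "Assuming that 10% of all randomized subjects will not be included in the primary endpoint analysis" as the number lost from the responder denominator. Read with mITT and LOCF it could mean that. But Protocol 7.1 and SAP 2.2 describe the 40 per arm as subjects who finish 12 weeks of treatment, so the 10% may include later dropouts, who remain in mITT as non-responders. It is therefore a ceiling.

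The protocol states the mITT exclusion openly and the SAP follows it, so this is a design choice and not a contradiction between the documents. That stands as well. The endpoint is secondary and the planned power does not rest on it.

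Finally, the all-randomised percentages and Fisher tests can be rebuilt from planned output: responder counts by arm (SAP 7.6.5.2) and numbers randomised and in each population (SAP 7.2). That is true, but it leaves the more complete estimate to be worked out after the results are seen, and the logistic model would still need refitting.

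**Conclusion.** The point holds as a modest inconsistency in a secondary analysis. Non-responder imputation is applied to a population that has already removed some of the subjects it is meant to cover, and a suitable population is already defined.

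The size is probably small. Under the illustrative assumptions, one or two exclusions on one active arm alone move the difference by 1.2 or 2.5 points, and four per arm, the upper reading of the planned loss, by 2.2 points (unrounded). If every randomised subject has a post-randomisation UACR, nothing changes. The figures rest on zero mean change on placebo, the sample-size effect and SD, and complete Week 12 data within mITT. None of these is stated for this endpoint.

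A reader might infer that the mITT analysis favours TMX-049. The documents do not support that: nothing in them says which arm will lose more subjects before any UACR, and greater loss on placebo makes the mITT difference too small. Nor do they give grounds for large, lopsided early losses on active drug.

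**What to change.** In SAP 7.6.5.2, run the Fisher tests and the logistic model on the Randomized population (SAP 5.2), with every subject lacking a Week 12 UACR counted as a non-responder. Keep the mITT result as supportive, and show the number excluded from mITT by arm beside it. Record the change in SAP Section 8, which now reads as not applicable, because Protocol 7.10.2 names mITT for efficacy.

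If the sponsor prefers to leave the protocol population in place, add the all-randomised version as a prespecified sensitivity analysis. That needs no departure from the protocol.

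The cost is a sentence or two in the SAP and one more run of the existing programs, with no new data, visit or population. The downsides are slightly lower responder rates in any arm with excluded subjects and, for the main fix, a documented departure from the protocol's mITT population for this one secondary endpoint.
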